5. Smoke Free Homes increase success in quitting. Evidence from cross-sectional and longitudinal studies shows an association between having a smoke free home and making a quit attempt, longer duration of quit attempts, and abstinence from smoking. Having a smoke free home is also associated with reduced relapse among ex-smokers and reduced cigarette consumption among continuing smokers. This is in part because smokers most likely to have home smoking bans are lighter smokers or in advanced stages of readiness to quit, but also due to genuine "treatment effects" like reducing exposure to smoking and other smokers, making it less convenient to smoke at home, and disrupting smoking patterns and cues.

To understand how establishing a smoke free home affects cessation in low-income smokers, we analyzed data from our team's Smoke Free Homes intervention trials (pooled n=941 with no home smoking ban at baseline). Controlling for study group and correlates of cessation and Smoke Free Homes, creating a Smoke Free Home increased quit rates at 3-month follow-up nearly 4-fold (15.6% vs 4.5%; OR=3.9, 95% CI=2.1,7.3) and even more at 6-month follow-up (26.1% vs 5.1%; OR=6.6, 95% CI=4.1,10.3). Most promising for the proposed study, among smokers who had never tried quitting at baseline, those who created a Smoke Free Home were significantly more likely to report a quit attempt at follow-up than those who did not create one.

6. Expanding treatment offerings in population-level tobacco services will attract more low-income smokers. Business scholars have shown that because customer needs and preferences vary, offering a variety of products or services attracts more customers and increases sales. These principles apply to reducing smoking in low-income Americans; by offering Smoke Free Homes, quitlines will engage more smokers than with cessation alone. NCI's Tobacco Control Research Priorities for 2016-2025 call for testing "population wide approaches" that increase "uptake and reach of existing evidence-based treatments" (Priority 1-1).

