Given the consistent intervention effects across three separate RCTs in over 1,500 households, we launched a dissemination trial in five 2-1-1s in four states (AL, FL, OH, OK) selected through a competitive RFA process to deliver SFH for one year and track outcomes. They enrolled 2,345 households, delivered SFH, and reached 1,543 households (66%) at 2-month follow-up; 61% reported a home smoking ban and 11% reported quitting.

Three secondary findings from these studies are highly relevant to the proposed study. First, although changes in smoking are not addressed by SFH nor were aims of the studies, all three RCTs found greater reductions in cigarettes smoked per day at follow-up in the SFH group (-2.9 per day) vs. controls. Confidence in quitting was higher at 3-month follow-up in the SFH vs. control group, and there were more quit attempts. In all study groups, those creating a home smoking ban had higher quit rates (see above). These findings bolster our claim that a smoke free home can help smokers progress towards quitting. Second, in all RCTs, the control group established home smoking bans at a high rate. We believe this was due to an extensive battery of questions they answered about home smoking bans at three time points (87 items in Atlanta; 96 in NC; 139 in TX). This "intervention via assessment" led to family discussions and thoughts about home smoking bans. In the current study, we avoid such reactance by asking <5 SFH questions see "Measures").

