 Based on previous research, in both groups, 25% of participants will accept QL when offered (Pilot 1, ongoing cessation R01); 42%, 31% and 27% will take 0, 1 and 2+ QL calls, respectively (ongoing cessation R01); and 12%, 13% and 31% will report quitting, respectively (ongoing cessation R01). In the QL+SFH group, 65% of those who decline QL will accept SFH (Pilot 2, SFH trials); of those accepting, 37% will create a SFH and 63% will not, with corresponding quit rates of 26% and 5% (SFH trials). We assume all who decline QL and SFH will quit at a very low rate (2%). Using these data to estimate cessation after a first offer of QL and SFH yields intent-to-treat quit rates of 5.9% (SFH) and 11% (QL+SFH). Even if no other cessation occurs, the study is powered to detect this difference. If we assume the same intervention use and quit rates apply for a second offer of QL and SFH (at 3-month follow-up), intent-to-treat quit rates would be 9.6% (SFH) and 17.5% (QL+SFH), also within the study's power. We are confident that the final quit rates for each group will fall between these values.

We used G\*Power to calculate the sample size required to detect study group quit rate differences of 6 vs 11% (minimum expected), 8 vs 14%, and 10 vs 17% (maximum expected) at three levels of power. As shown, with 1,116 participants (558 per group) completing 6-month follow-up, we can detect a 6 vs 11% difference with 85% power. Power will be greater for larger differences. Attrition is expected to be 40% at 6-month follow-up, thus a baseline sample of 1,980 assures enough participants at follow-up (n=1,188) even if attrition is slightly higher than projected.

**1.23** Will any data from this project be stored for use in future research studies?  
 Yes - contribution for future use is mandatory for participation in the study

**1.24** Does this project involve the collection or use of biological samples or genetic data?  
 No

**1.25** Are you requesting institutional certification to contribute human data or samples to a repository or database for broad sharing (public or restricted access)?  
 No

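### The first-offer planning rates (5.9% vs 11%) give comparable people without a home ban 2% in the control arm and 5% in Arm 2; with equal rates, first-offer power is 76% to 59%, so 6 vs 11% at 85% is not a minimum

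*Combined protocol and SAP*

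**What the plan says.** Section 1.21 builds the quit rates from these inputs. In both arms 25% accept the Quitline (QL). Of these, 42%, 31% and 27% take 0, 1 and 2+ calls and quit at 12%, 13% and 31%. In Arm 2, 65% of those who decline QL accept SFH; of the acceptors, "37% will create a SFH and 63% will not, with corresponding quit rates of 26% and 5% (SFH trials"). For the remainder: "We assume all who decline QL and SFH will quit at a very low rate (2"%).

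The resulting first-offer intention-to-treat rates are 5.9% and 11%. (The text labels the lower rate SFH; it can only be the QL-only arm.) The section then says: "Even if no other cessation occurs, the study is powered to detect this difference". The sample size rests on "quit rate differences of 6 vs 11% (minimum expected"), with 558 completers per group giving 85% power. A second scenario, after a repeat offer at 3 months, gives 9.6% and 17.5%, followed by "We are confident that the final quit rates for each group will fall between these values".

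The 26% and 5% match claim 5 of the background (section 1.5), an analysis of the pooled SFH trials by ban status: "Controlling for study group and correlates of cessation and Smoke Free Homes, creating a Smoke Free Home increased quit rates" at 3 months and "even more at 6-month follow-up (26.1% vs 5.1%; OR=6.6, 95% CI=4.1,10.3"). Later, section 1.5 adds: "In all study groups, those creating a home smoking ban had higher quit rates (see above").

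**The concern.** Section 1.21 gives no quit rate for controls who decline QL. The 2% is defined for people who decline both programmes, and controls are offered only one. The 5.9% nevertheless requires 2% for all of them. Randomization makes about 65% of control decliners people who would have accepted SFH if asked. In Arm 2 those people get 5% even when they create no ban.

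The 5% is not shown to be an effect of receiving SFH. Its apparent source compares people with and without a ban, adjusting for study group, and the ban difference was seen in every study group. Using 5% in one arm and 2% in the other therefore adds an unstated treatment effect to the planned difference.

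At stake is the claim that 6 vs 11% is a minimum for which the study is powered even if nothing beyond the first offer produces quitting. If that figure depends on a favourable unstated assumption, it is not a minimum.

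**Working it through.** **Inputs.** All rates are from section 1.21. Alpha and sidedness are not in the available text; I assume a two-sided 5% two-proportion z test with pooled variance under the null. For 6 vs 11% at 85% power this gives exactly 558 per group (a one-sided test gives 446, a continuity correction 597), and power at 558 is 85.1%. The plan expects 1,188 completers, or 594 per arm.

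**The plan's own rates.**
- QL acceptors: 0.42×0.12 + 0.31×0.13 + 0.27×0.31 = 0.1744; contribution to each arm 0.25×0.1744 = 0.0436.
- Control: 0.0436 + 0.75×0.02 = 0.0586. This is the stated 5.9%, with 2% for every QL decliner.
- Arm 2: 0.0436 + 0.75×[0.65×(0.37×0.26 + 0.63×0.05) + 0.35×0.02] = 0.1111.
- Difference 5.25 points. Power at these unrounded rates is 88% at 558 and 90% at 594.

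**Size of the mismatch.**
- Credit given to Arm 2 acceptors without a ban: 0.75×0.65×0.63×(0.05−0.02) = 0.92 points, 17.5% of 5.25.
- If control would-be acceptors also get 5%: 0.75×0.65×(0.05−0.02) = 1.46 points lost.

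**Same no-ban rate r for would-be SFH acceptors in both arms; 2% for those who decline, or would decline, both.**
- Control: 0.0436 + 0.75×(0.65r + 0.35×0.02)
- Arm 2: 0.0436 + 0.75×[0.65×(0.37×0.26 + 0.63r) + 0.35×0.02]

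| r | Control | Arm 2 | Difference (points) | Power, 558 per arm | Power, 594 per arm |
|---|---|---|---|---|---|
| 2% | 5.86% | 10.19% | 4.33 | 76% | 78% |
| 3% | 6.35% | 10.50% | 4.15 | 70% | 73% |
| 4% | 6.83% | 10.80% | 3.97 | 65% | 67% |
| 5% | 7.32% | 11.11% | 3.79 | 59% | 62% |

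A literal 5% for every decliner without a ban, including those who decline both, gives 8.1% vs 11.9% and power 56% (59% at 594).

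**Contact effect needed to keep 85%.** With control decliners at 2%, the Arm 2 no-ban rate must be at least 4.0% at 558 per arm (3.5% at 594), an effect of about 2.0 points (1.5). With Arm 2 held at 5%, 85% holds only while control would-be acceptors quit at 2.5% or less (2.7% at 594).

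**After the second offer, 558 per arm.** Section 1.21 assumes that the second offer works like the first but does not show its method. Full compounding of its first-offer rates gives 1−(1−0.0586)² = 11.4% and 1−(1−0.1111)² = 21.0%, not 9.6% and 17.5%. I therefore used three versions: the plan's own second-to-first ratios (0.096/0.0586 = 1.638 and 0.175/0.1111 = 1.575); a second offer reaching 73%, the 3-month follow-up rate in section 1.5, p + (1−p)×0.73×p; and full compounding, p + (1−p)×p.

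| r | Plan ratios | 73% reached | Full compounding |
|---|---|---|---|
| 2% | 90% | 93% | 96% |
| 3% | 85% | 89% | 93% |
| 4% | 80% | 85% | 90% |
| 5% | 74% | 80% | 86% |

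**The case against.** The strongest reply is that the first-offer case is hypothetical. The primary outcome is 6-month abstinence, measured after a scheduled second offer at 3 months, where power is at least 85% at no-ban rates of 2% and 3%. This stands, and it rules out calling the trial underpowered on this ground. It does not rescue the separate claim that the study is powered on the first offer alone.

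Second, SFH contact may help people who create no ban. Section 1.11 gives acceptors a coaching call and three mailings, and section 1.5 reports more quit attempts, more confidence in quitting and larger cigarette reductions in the SFH groups. This also stands as a possibility. But those results are not given separately for people without a ban, the pooled 5.1% is not split by arm, and section 1.21 states no such effect.

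Third, 5% for controls is weakly supported. The SFH trial controls answered 87 to 139 items on home bans, and section 1.5 expects less effect of assessment here. So 59% is one end of a range and not a best estimate; even the favourable end gives 76%.

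Fourth, the recalculation is itself conditional: it keeps 26% for ban creators and assumes no bans among control decliners. That is true, but allowing control bans lowers power further. As an illustration, a ban in 10% of control would-be acceptors gives 47% (r = 2%) or 34% (r = 5%).

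Finally, the 74% after the second offer rests on ratios from figures that do not rebuild by simple compounding, so it is fragile. Hence the range.

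**Conclusion.** The concern holds. The plan's 5.9% vs 11% includes 0.92 of its 5.25 points as credit to SFH acceptors without a ban, with no stated reason why they should quit more often than comparable controls. With equal no-ban rates, first-offer power is 76% to 59% at 558 per arm and stays below 85% across the whole 2–5% range, including at 594 per arm. Calling 6 vs 11% a minimum is correct only if SFH contact without a ban adds about 2 points over control decliners at 2% (1.5 points at 594).

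This rests on an inferred two-sided 5% test, on the inference that control decliners were set to 2% (the only value that returns 5.9%), and on a numerical match between the 5% and the pooled trial analysis. The documents support a range and not either end. Power at the 6-month endpoint, after the second offer, is about 74% to 96%.

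**What to change.** In section 1.21, use one no-ban quit rate for would-be SFH acceptors in both arms and 2% for those who decline or would decline both. Present 2–5% as a sensitivity range (76% to 59% at 558 per arm) without naming either end the base case. Alternatively, keep the two rates but state the SFH-contact effect they imply, with its size and justification.

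Beside this, show power after the 3-month second offer, with the method by which 9.6% and 17.5% were obtained (about 90–96% at a no-ban rate of 2%, 74–86% at 5%). Remove the minimum-case label, the claim of adequate power without further cessation and the statement of confidence, or make each conditional on the stated assumption.

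The cost is one rewritten paragraph and one small table. The stated first-offer power becomes less favourable; enrolment and procedures do not change.

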## 2. Participants

---

**2.1** Will there be any adult participants?  
 Yes

**2.1.a** How many adult participants do you expect to consent or enroll under a waiver for this project?  
 1980

**2.1.b** What is the age of the youngest adult participant?  
 21.0

**2.1.c** What is the age of the oldest adult participant?  
 No age limit

**2.2** Will there be any minor participants?  
 No

**2.3** Will there be any emancipated minor participants?  
 No

**2.7** Do you plan to recruit/enroll non-English speaking people?  
 No

**2.8** Do you propose to enroll any of the following in this study as participants?

- Employee of the PI or employee of a research team member

- Individual supervised by PI or supervised by member of research team
- Individual subordinate to the PI or subordinate to any member of the research team
- Student or trainee under the direction of the PI or under the direction of a member of the research team

No

**2.9** Is this project about pregnant women?

No

**2.10** Will this project involve fetuses?

No

**2.11** Does this project involve the use of fetal tissue from any source?

No

**2.12** Does this project recruit adult participants who may be incompetent or have limited decision-making capacity on initial enrollment into the study?

No

**2.13** Does this project involve prisoners as participants?

No

### 3. Performance Sites

**3.1** Indicate type of site(s) where research will occur (check all that apply):

- Academic Institution

**3.2** Where will project procedures take place (check all that apply)?

- Danforth Campus
- U.S. off-campus - Optum will conduct the Quitline services via phone; United Way 2-1-1's across 9 states will be recruiting over the phone.

**3.3** Is this project also being conducted by other researchers at their own sites (e.g. a multi-site collaborative project)?

Yes

**3.3.a** What is your site's role(s) for this project (check all that apply)?

- Coordinating Center

**3.3.b** Indicate the requirements for participating sites to report unanticipated problems to the coordinating center/lead site:

Timeframe	Contact Method
• Within 1 week	• Email • Phone

**3.3.c** Indicate the requirements for the lead site to report unanticipated problems to the participating sites:

Timeframe	Contact Method
• Within 2 weeks	• Email • Phone

**3.3.d** Indicate the requirements for the lead site to communicate protocol modifications to the participating sites:

Timeframe	Contact Method
• Greater than 2 weeks	• Email • Phone

**3.3.e** Indicate the requirements for the lead site to communicate interim results to the participating sites:

Timeframe	Contact Method
• Greater than 2 weeks	• Email • Phone

**3.3.f** Indicate the requirements for the lead site to communicate other new information to the participating sites:

Timeframe	Contact Method
• Greater than 2 weeks	• Email • Phone

**3.3.g** What are participating site roles for this project?

- Other - Representatives from Emory University will listen to audio recordings of the Smoke-Free Homes coaching call and provide feedback to the coach(es).

**5. Privacy & Confidentiality**

---

**5.1** Indicate your plans to protect the privacy interests of the participants during the conduct of the study (check all that apply):

- Only the minimum necessary private information is collected for the purposes of the study
- Any procedures or interventions conducted as part of the study will be conducted in private setting to the extent possible
- Recruitment/consent will occur in a private setting
- Participants will be able to ask questions in a private setting

**5.2** Are you collecting or using the Social Security Number of any participants for any purpose?

Yes

**5.2.a** Provide the intended usage of SSN:

- To provide compensation to participants

**5.3** Project uses paper or hard copy consents, surveys, data collection forms, research subject binders, or other hard copy materials (check all that apply):

No

**5.4** Project collects, stores and/or transmits electronic data on mobile devices, desktop computers, servers including cloud servers, email, or any other information in electronic form (check all that apply):

Yes

- Data are encrypted
- Password protected
- Access is limited to research team only

**5.5** Project collects or uses biologic specimens (check all that apply):

No

**5.6** Identify any additional protections in place for data and or samples (check all that apply):

- Data Use Agreement (DUA)
- Formal research staff training process
